6.1 Data and Safety Monitoring Board

This study will use a Data and Safety Monitoring Board (DSMB). The plan is to perform an initial PK analysis after the first 3 participants are enrolled in the single dose PK arm and also after the first 3 participants are enrolled in the steady-state pharmacokinetic arm. The data will be reviewed by the DSMB to assess for safety to continue the single-dose pharmacokinetic study and to continue the steady-state pharmacokinetic study.

7. Protection of Human Subjects

7.1 Investigator Responsibilities

The investigator is responsible for ensuring that the study is performed in accordance with the protocol, current ICH guidelines on Good Clinical Practice (GCP), and applicable regulatory and country-specific requirements.

Good Clinical Practice is an international ethical and scientific quality standard for designing, conducting, recording, and reporting studies that involve the participation of human subjects.

Compliance with this standard provides public assurance that the rights, safety, and well-being of study subjects are protected, consistent with the principles that originated in the Declaration of Helsinki, and that the study data are credible.

7.2 Institutional Review Board and FDA Submissions

The protocol, informed consent form(s), recruitment materials, and all participant materials will be submitted to the IRB for review and approval. Approval of both the protocol and the consent form must be obtained before any participant is enrolled. Any amendment to the protocol will require review and approval by the IRB before the changes are implemented to the study. All changes to the consent form will be IRB approved; a determination will be made regarding whether previously consented participants need to be re-consented.

During the study, the investigator will send the following documents and updates to the FDA for their review and the IRB for their review and approval, where appropriate:

- Protocol amendments (excluding the ones that are purely administrative, with no consequences for subjects, data, or study conduct).
- Revision(s) to ICF and any other written materials to be provided to subjects.
- Summaries of the status of the study at intervals stipulated in guidelines of the IRB and the FDA (at least annually).
- Reports of AEs that are serious, unlisted/unexpected, and associated with the study drug.
- New information that may adversely affect the safety of the subjects or the conduct of the study.
- Deviations from or changes to the protocol to eliminate immediate hazards to the subjects.
- Report of deaths of subjects under the investigator's care.
- Notification if a new investigator is responsible for the study at the site.
- At least once a year, the IRB will be asked to review and reapprove this study, where required. An annual report will be submitted to the FDA.
- At the end of the study, the investigator will notify the IRB and the FDA about the study completion

7.3 Informed Consent Form

Written permission from parents or legal guardians will be required for participation. Parental consent will also be required. After determining that a subject is eligible, the site investigator or designee will approach the parent or legal guardian to offer participation in the study. The parent or legal guardian will be informed about the objectives of the study and the potential risks and benefits of participation. If the parent or legal guardian refuses consent to participate OR refuses permission for their infant to participate, then all clinical management for the infant will be provided by the clinical staff in accordance with institutional practice and judgment.

7.3.1 Child Assent

Subjects who are eligible for this study are under 6 months of age and assent is not applicable.

7.4 Adverse Event Reporting

7.4.1 Assessment of Safety

Safety assessments will consist of monitoring and reporting adverse events (AEs) and serious adverse events (SAEs) per protocol for 48 hours after the last study drug dose. This includes all events of death, and any study specific issue of concern.

7.4.2 Adverse Events

Investigators must report all potential unanticipated problems and events to the IRB. Unanticipated problems (UPs) are defined as *any incident, experience or outcome that meets all of the following criteria:*

- **Unexpected** (unforeseen by the researcher or the research participant) in terms of nature, severity, or frequency, given the research procedures and the subject population being studied;

and

- **Related or probably** related to participation in the research, or if the event or problem probably or definitely affects the safety, rights and welfare of current participants;

and

- Suggests that the research places subjects or others at a **greater risk of harm** (including physical, psychological, economic or social harm) than was previously known or recognized.

The Investigator must consider each problem, event, or new information and decide whether or not it represents a UP, using the criteria above.

In fatal or life-threatening serious adverse events, either unexpected and unrelated, or suspected to be related to the study, notification will be sent to the DSMB Chair, the IRB, and NHLBI program office within 7 calendar days of the PI becoming aware of the event.

In non-fatal, non-life-threatening serious adverse reactions either unexpected and unrelated, or suspected to be related to the study, notification will be sent to the DSMB Chair, the IRB, and NHLBI program office within 14 calendar days of the PI learning of the event.

In both cases, the DSMB chair will review the event, determine if a full DSMB meeting should be held, and will respond to the PI and NHLBI program office with recommendations within 3 business days of notification.

Unanticipated problems that are not a serious adverse event (SAE) will be reported to the IRB, DSMB, and NHLBI within 14 days of the PI becoming aware of the problem.

If UP Criteria Are Not Met:

1. Document in the research record how the problem/event/information does not meet the UP Criteria.
2. Summarize the problem/event/information in the next Continuing Review application.

Examples of Potential Unanticipated Problems

- A breach of confidentiality or privacy that involves real or potential risk (e.g. unauthorized use of disclosure of protected health information.)
- Data and safety monitoring reports that indicate that frequency or magnitude of harms or benefits may be different than initially presented to the IRB
- A publication that shows that the risks or potential benefits or the research may be different than initially presented to the IRB
- Change in FDA labeling or withdrawal from marketing of a drug, device, or biologic used in a research protocol
- Complaints from participants or others involved in the research that indicate unexpected risks or cannot be resolved by the research team
- Warning or determination letters issued by any funding agency or regulatory body including Office of Human Research Protections (OHRP), Department of Health and Human Services (DHHS), Food and Drug Administration (FDA)

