5.3.6 Participant monitoring

All participants will be monitored for clinical evidence of necrotizing enterocolitis, gastrointestinal bleeding, sepsis, feeding intolerance (including vomiting and diarrhea), electrolyte disturbances, hemodynamics, alteration of hematological parameters and death. Any electrolytes, hematologic laboratories, and eye examinations that are ordered as part of standard of care by the participants clinical care team will be monitored. Hypotensive subjects (defined as a decrease in mean arterial blood pressure of more than 25% baseline) will be treated with pharmacological/volume supplementation interventions at the discretion of the attending physician. Treatment unresponsive hypotensive subjects will be withdrawn from the study. Subjects who develop significant feeding intolerance will be withdrawn from the study. Infants who are made NPO for a time period long enough that they miss any doses of L-citrulline will be withdrawn from the study.

6. Statistical Methods, Data Analysis and Interpretation

After the first 3 participants are enrolled in the single-dose PK study (3 participants enrolled in either Group 1 or Group 2), and after the first 3 participants are enrolled in the steady-state pharmacokinetic study (3 participants enrolled in Group 3), an initial PK analysis will be performed and the data will be reviewed by the DSMB to assess for safety to continue the single dose PK study and to continue the steady-state pharmacokinetic study.

Throughout the study, participants who are withdrawn from treatment due to adverse events will be replaced for PK analysis.

Data collected from this study will be examined to ensure that all participants in the analysis meet inclusion criteria. Summary statistical analysis will be conducted to describe participant demographics, citrulline dosing, and participant PK profiles. Outliers in the measured citrulline levels that may influence the estimation of PK parameters will be evaluated. A population model will be developed to describe the citrulline PK and population variability.

The non-linear mixed effect modeling software NONMEM® version 7.3.0 (ICON Development Solutions, [name], USA) will be used to develop models. Perl-speaks-

NONMEM (PsN) 4.4.0, Pirana 2.9.0, and R packages (version 3.2.1) will be used to facilitate, evaluate, and visualize the model development.

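### Serious events judged expected and unrelated do not go to the DSMB, and no Group 3 review is scheduled after the first 3 infants, so what the board learns depends on the investigator's classification

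*Combined protocol and SAP*

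**What the plan says.** All references are to the combined protocol and SAP.

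- **Hazards.** Section 5.3.6 has all participants "monitored for clinical evidence of necrotizing enterocolitis, gastrointestinal bleeding, sepsis, feeding intolerance (including vomiting and diarrhea"; the list goes on to electrolytes, hemodynamics, hematological changes and death. It does not say that counts of these go to the DSMB.
- **Serious events, 7-day rule (7.4.2).** For fatal or life-threatening cases the condition and first recipient read: "either unexpected and unrelated, or suspected to be related to the study, notification will be sent to the DSMB Chair". The time limit is 7 calendar days, and the same notice goes to the IRB and the funder's program office.
- **Serious events, 14-day rule (7.4.2).** "In non-fatal, non-life-threatening serious adverse reactions either unexpected and unrelated, or suspected to be related to the study", with the same recipients. This sentence speaks of reactions where the 7-day rule speaks of events.
- **Non-serious events (7.4.2).** "Unanticipated problems that are not a serious adverse event (SAE) will be reported to the IRB, DSMB, and NHLBI within 14 days". To be an unanticipated problem, an event must be unexpected, related (or affect participants' safety, rights or welfare), and suggestive of greater risk, all together.
- **Meaning of unexpected (7.4.2).** It is judged "in terms of nature, severity, or frequency, given the research procedures and the subject population being studied".
- **Extra meetings (7.4.2).** Once notified, "the DSMB chair will review the event, determine if a full DSMB meeting should be held".
- **Scheduled review (6 and 6.1).** For Group 3 there is one, "after the first 3 participants are enrolled in the steady-state pharmacokinetic arm". No later review, interval or cumulative listing is given.

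**The concern.** The hazards in section 5.3.6 are ones that a clinician could readily attribute to prematurity in infants born at 28 weeks or earlier who still need respiratory support. A single case can reasonably be classed as expected and unrelated, and that is the one combination for which section 7.4.2 gives the DSMB no notice. With no control group, no list of expected events and no background rates, nothing in the plan lets anyone check that classification.

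Tolerability over 72 hours of dosing is a primary objective (2.2.1), and section 1.6 says the results will be used to design a multi-center efficacy trial. Groups 1 and 2 received one dose each and Group 3 receives twelve, so the single-dose experience does not cover repeated dosing. If several cases were classed one at a time as background, the board asked to judge whether it is safe to continue might not see them together.

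**Working it through.** **1. Counts.** Section 3.2 gives 5 + 5 + 18 = 28, which reproduces the stated total. Infants in Group 3 beyond the 3 that trigger the review: 18 − 3 = 15, and 15/18 = 83%. Fifteen is a minimum, because section 6 replaces participants withdrawn for adverse events.

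**2. Routing of serious events under 7.4.2.** The rule is: notify if (unexpected and unrelated) or (suspected related).

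| | Judged unrelated | Suspected related |
|---|---|---|
| Expected | not sent | sent |
| Unexpected | sent | sent |

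Three of the four cells reach the DSMB Chair.

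**3. Does another route carry the missing cell to the DSMB?**
- Unanticipated-problem route (7.4.2): no, since the event must be unexpected.
- Events failing those criteria (7.4.2): research record and next Continuing Review; the DSMB is not named.
- Deaths (7.2): IRB and FDA; the DSMB is not named.
- Safety assessment to 48 hours after the last dose (7.4.1): covers deaths and events, but names no recipient.
- Expedited FDA reports (7.4.3): only serious, unexpected suspected reactions.
- Unscheduled full meeting (7.4.2): its stated trigger is a notified event.

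None does.

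**4. How much a 3-infant review can show.** The documents give no event rates. The rates p below are assumptions for illustration.

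| Assumed p per infant | At least 1 case in first 3: 1 − (1 − p)³ | Expected cases in next 15: 15p | No case in first 3, then at least 2 in next 15 |
|---|---|---|---|
| 5% | 14% | 0.75 | 0.857 × 0.171 = 15% |
| 10% | 27% | 1.5 | 0.729 × 0.451 = 33% |
| 20% | 49% | 3.0 | 0.512 × 0.833 = 43% |

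The last column multiplies (1 − p)³ by the exact binomial probability of at least 2 in 15.

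With no events in n infants, the one-sided 95% upper bound on the rate is 1 − 0.05^(1/n): 63% for n = 3, 28% for n = 9 and 15% for n = 18.

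These figures show how little three infants can rule out. They do not give the probability that an event escapes the DSMB, which depends on classification and cannot be computed from the documents.

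**The case against.** A reader might infer that an excess of necrotizing enterocolitis or sepsis would pass unseen and that the DSMB would not receive it. The documents do not support that, for four reasons.

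- Unexpectedness in 7.4.2 includes frequency, so an investigator who recognises an excess can call it unexpected and notify the Chair even if each case is judged unrelated.
- Events suspected to be related go to the Chair even when expected. Gut disease arising during 72 hours of enteral dosing or the next 48 hours is a natural candidate.
- Section 3.4 excludes prior necrotizing enterocolitis, significant feeding intolerance beyond the first week, acute illness and infants anticipated to die before discharge. A death in an infant screened this way is hard to call expected.
- The investigator sees every event, deaths go to the IRB and FDA, and events that are not unanticipated problems are summarised at Continuing Review.

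All four stand, and they limit the point to what the DSMB sees. They do not close the gap: the first two rest on the judgement that an independent board is there to check, and the plan supplies no reference rate for deciding when a frequency is unexpected.

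Two further arguments carry some weight. The planned PK analysis is described as an initial one, and the DSMB approved cutting Groups 1 and 2 to 10 infants (3.2), so further contact is plausible; still, none is scheduled for Group 3. Also, with 0.75 to 3 expected cases and no controls, a listing could rarely separate excess from background statistically. That is true, but its purpose is independent clinical review of the cases together, which needs no test.

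**Conclusion.** The point holds in a limited form. Section 7.4.2 as worded omits serious events that are both expected and judged unrelated, and no other section sends them, or cumulative counts, to the DSMB. After the one scheduled review, what the board learns about the named hazards in at least 15 of 18 Group 3 infants depends on the investigator's classification. This is a gap in a stated rule and should be corrected. It is not evidence that harm would go unnoticed, since the investigator, IRB and FDA each hold part of the information.

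The count of 15 and the routing table rest on the text alone. The 14%, 27% and 49% figures rest on assumed rates of 5%, 10% and 20%, which are not tied to serious events within the roughly five-day observation window (72 + 48 = 120 hours), and serve only as illustration.

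**What to change.** 1. **Section 7.4.2.** Send every serious event on the 5.3.6 list to the DSMB Chair on the existing 7- and 14-day clocks, regardless of expectedness or attribution. Use the term events in both sentences. All four cells of the routing table are then covered for the listed hazards.
2. **Section 6.1.** Add at least one cumulative listing to the DSMB during Group 3, covering all 5.3.6 events, serious and non-serious, together with withdrawals. Non-serious entries are needed because feeding intolerance will often not meet the definition of serious, so the first change alone would miss it. The documents do not fix a time; about the midpoint is one option. After 9 infants, the chance that at least one case has occurred is 1 − (1 − p)⁹ = 37%, 61% or 87% at the assumed 5%, 10% or 20%, against 14%, 27% or 49% after 3. Enrolment need not pause.

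The cost is protocol wording, one short listing to a board that already exists, and a few extra notifications of background events. No dose or clinical rule changes.

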- For Group 1: one blood draw will be pre-dose and 2 blood draws will be post-dose. The pre-dose blood draw will occur 24-48 hours prior to administering the dose of oral L-citrulline and the two post-dose draws will occur at 1 hours (+/- 10 minutes) and 2.5 hours (+/- 10 minutes) post-dose.
- For group 2: one blood draw will be pre-dose and 2 blood draws will be post-dose. The pre-dose blood draw will occur 24-48 hours prior to administering the dose of oral L-citrulline and the two post-dose draws will occur at 15 minutes (+/- 10 minutes) and 3 hours (+/- 10 minutes) post-dose

These sampling times are designed to estimate the population PK parameters of a typical infant using scaling and population PK analysis of available oral PK profiles in adults (28).

The single dose pharmacokinetic studies have been completed. PK data from 10 subjects (5 in group 1 and 5 in group 2) were analyzed and assessed as being sufficient to provide the information needed to design the next phase, the steady state pharmacokinetic studies.

5.3.2 Steady-state pharmacokinetic studies:

To evaluate the tolerability and ability to achieve target trough L-citrulline levels of 50-80 μ M, an additional group of 18 infants (group 3) will be given oral L-citrulline doses at intervals over a total of 72 hours. The L-citrulline will be provided by Asklepiion Pharmaceuticals. If the participant is not nipple feeding, the dose will be

delivered via the participant's indwelling gavage feeding tube. The dose and interval of L-citrulline are based on results from the studies that assessed pharmacokinetic parameters using a maximum daily dose of 3 g/kg/d. The choice of the maximum daily dose is based on a recent study that showed good tolerability and reported no adverse effects in children with mitochondrial encephalomyopathy, lactic acidosis and stroke-like episodes (MELAS syndrome) treated with oral l-citrulline at a dose of 3 g/kg/d (500 mg/kg/dose given every 4 hours) (37).

Based on results from the single dose pharmacokinetic studies, the infants in group 3 will be given oral L-citrulline doses of 60 mg/kg every 6 hours +/- 30 minutes (4 times a day) for 72 hours (total of 12 doses). This is a total daily dose of 240 mg/kg/day.

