7.4.3 Mandatory FDA Safety Reporting

Initial reporting:

The IND application sponsor investigator must report any suspected adverse reaction or adverse reaction to study treatment that is both serious and unexpected as soon as possible but no later than within **15 calendar days** following the sponsor's initial receipt of the information

Unexpected fatal or life-threatening suspected adverse reactions represent especially important safety information and must be reported to FDA as soon as possible but no later than **7 calendar days** following the sponsor's initial receipt of the information.

- **Follow-up reporting:** Any relevant additional information obtained by the sponsor that pertains to a previously submitted IND safety report must be submitted as a Follow-up IND Safety Report. These reports should be submitted without delay, as soon as the information is available but no later than 15 calendar days after the sponsor receives the information.

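### After a fatal or life-threatening event suspected to be related, 10 to 12 days may pass before the DSMB Chair's reply is due, and nothing pauses new starts meanwhile

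*Combined protocol and SAP*

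**What the plan says.** Section 7.4.2 sets the timetable. Its faster track applies "In fatal or life-threatening serious adverse events, either unexpected and unrelated, or suspected to be related to the study". For these events the DSMB Chair is notified together with the IRB and the "NHLBI program office within 7 calendar days of the PI becoming aware of the event". The Chair reviews the event, decides whether the full board should meet, and "will respond to the PI and NHLBI program office with recommendations within 3 business days of notification". No deadline is given for a full meeting.

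Sections 5.3.2 and 6 give the Group 3 regimen as doses "every 6 hours +/- 30 minutes (4 times a day) for 72 hours (total of 12 doses". Group 3 has 18 infants (section 3.2), recruited at three hospitals (section 5.1).

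Sections 6 and 6.1 schedule one DSMB review in Group 3, "also after the first 3 participants are enrolled in the steady-state pharmacokinetic arm". It concerns whether it is safe to continue, but it is triggered by an enrolment count and no pause in enrolment is stated.

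**The concern.** Seven days is a reporting limit, and as a reporting limit it is unremarkable. The difficulty is that the protocol gives no separate rule on what happens to enrolment while the report is on its way and under review. The course being tested is short compared with the reporting limit. A site could follow section 7.4.2 exactly and still take further infants through the whole regimen before the Chair has to be told of a death suspected to be due to it.

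Groups 1 and 2 received a single dose, so Group 3 is this study's first repeated dosing. The protocol already asks the DSMB to judge safety to continue after 3 infants in this group. A death suspected to be related is a stronger reason to ask that question than reaching a count of 3, yet it has no comparable effect on whether the next infant starts.

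**Working it through.** **Inputs**
- Notice to the DSMB Chair: at most 7 calendar days from PI awareness (7.4.2).
- Chair's reply: at most 3 business days from notification (7.4.2).
- Group 3 course: one dose every 6 hours for 72 hours, 12 doses (5.3.2 and 6).
- Accrual rate: not given.

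**Length of a course**
- Number of doses: 72 / 6 = 12, which matches the protocol.
- First to last dose: (12 - 1) x 6 = 66 hours. This figure is derived; the protocol describes the course as 72 hours.
- With the 30-minute tolerance: 65 to 67 hours if it applies to nominal clock times, or 11 x 5.5 = 60.5 to 11 x 6.5 = 71.5 hours if it accumulates.

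**Length of the window**
- Three business days, counted from the day after notification and ignoring public holidays, are 3 calendar days for notice on a Sunday, Monday or Tuesday, 4 for a Saturday, and 5 for a Wednesday, Thursday or Friday.
- To notice: 7 x 24 = 168 hours.
- To reply: (7 + 3) x 24 = 240 hours up to (7 + 5) x 24 = 288 hours, or 10 to 12 calendar days.

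**Courses that fit, one infant at a time, back to back**

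| Window | Hours | / 66 h | / 72 h | Whole courses |
|---|---|---|---|---|
| Until the Chair must be told | 168 | 2.5 | 2.3 | 2 |
| Until reply due, shortest | 240 | 3.6 | 3.3 | 3 |
| Until reply due, longest | 288 | 4.4 | 4.0 | 4 |

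The whole-course counts also hold at the extremes of the tolerance. At 60.5 hours the ratios are 2.8, 4.0 (3.97, so 3 whole courses) and 4.8; at 71.5 hours they are 2.3, 3.4 and 4.0 (4.03).

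**Search for a pause on new starts**
- Section 5.3.6: the withdrawal rules act on the affected infant, for example "Treatment unresponsive hypotensive subjects will be withdrawn from the study".
- Sections 6 and 6.1: the review is tied to the third enrolment, not to an event. After it, up to 18 - 3 = 15 infants remain.
- Section 7.2: deaths and new safety information go to the IRB and the FDA, and changes to remove an immediate danger are provided for. These are reports and permissions.
- Section 7.4.3: "Unexpected fatal or life-threatening suspected adverse reactions represent especially important safety information and must be reported to FDA as soon as possible", with 7 calendar days as the outer limit. This is a report. Section 7.4.2 has no equivalent urgency for the DSMB Chair.
- Section 7.4.4: recognises departures made to protect a participant from immediate hazard. It permits action and does not require it.

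None of these requires new starts to wait.

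**The case against.** **The limits are maxima, and people can act sooner.** This is true. The clock starts at PI awareness, a PI may call the Chair the same day, and sections 7.2 and 7.4.4 leave room for a voluntary pause. What remains is that none of this is required.

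**Other bodies hear of the event.** A reader might infer that the DSMB timetable is the only link between a related death and a decision to continue. The documents do not support that. The IRB and NHLBI receive the same notice, and the FDA must be told of unexpected fatal or life-threatening suspected reactions. These are real routes to a decision, but none carries an automatic hold.

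**The number of infants exposed is unknown.** A reader might multiply 3.6 to 4.4 courses by three hospitals, get 11 to 13, and conclude that most of the 15 infants left after the DSMB review could be dosed before a reply. The documents do not support this either. Fractional courses are not completed ones: whole courses give 3 x 3 = 9 to 3 x 4 = 12. Nor is that an upper bound, since the protocol does not limit a hospital to one infant at a time. The implied pace is also hard to credit, because it would dose all 18 infants in 6 x 66 = 396 hours, or 16.5 days. The eligibility window is narrow, multiple births are excluded, and parents are encouraged to take the consent form home. At an assumed one infant per week overall, 10 to 12 days covers 1.4 to 1.7 starts; at one per month (30 days), 0.3 to 0.4.

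**A DSMB charter might contain a halting rule.** If one exists, it is not among the documents, and the protocol does not refer to one. The point is therefore about what the protocol states and does not show that oversight would fail in practice.

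**Conclusion.** The point stands as a gap in trial conduct that should be closed. Section 7.4.2 as written allows 10 to 12 calendar days from PI awareness to the Chair's reply, and no section holds new starts in that time. With one infant dosed at a time, that is room for 2 completed courses before the Chair need be told and 3 to 4 before a reply is due.

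The counts rest on three assumptions: both limits are used in full, infants start back to back from the moment of PI awareness, and there are no public holidays. They show what the text permits and are not a forecast. The 10 to 12 days is itself not the longest path to a decision, because a full DSMB meeting, if the Chair calls one, has no deadline.

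**What to change.** Add to section 7.4.2, for a fatal or life-threatening event suspected to be related:

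- From the time the PI becomes aware, no new infant starts study drug until the DSMB Chair has responded.
- The Chair is notified promptly and well inside the 7-day limit, for example within 1 business day. The documents give no basis for a particular interval, so the sponsor and DSMB should agree it.
- The Chair's 3 business days run from that first notice, so that a later fuller report does not restart the clock.

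The IRB and NHLBI deadlines stay as they are. The change concerns new starts only and does not address dosing or care of infants already on study.

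The cost is a few lines of text and a short enrolment pause after a rare event. With notice in 1 business day, the pause would last at most 1 + 3 = 4 business days (4 to 6 calendar days without public holidays), unless the Chair recommends otherwise. If accrual is slow, few or no starts would be delayed.
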